
Amendment 05
	
10 August 2021
 
153 patients have been randomized/enrolled to date
 
The following sections are affected:
 
Preface
 
Table 1 Study Procedures and Assessments
 
Section 4.1 Patient Inclusion Criteria
 
Section 4.2 Patient Exclusion Criteria
 
Section 5.7.1 Permitted Concomitant Medication or Therapy
 
Section 5.11 Total Blood Volume
 
Section 7.4.2.2 Urine Drug Screen
 
Section 9.6.4.2 Sensitivity Analysis
 
Section 9.15 Planned Interim Analysis
 
Appendix B Study Procedures and Assessments by Visit
 
Appendix I. List of Prohibited Medications and Therapeutic Interventions
 
Appendix J. Total Blood Volume
 
Appendix O. Management of Study Activities During COVID-19

---------------------	--

Amendment 04, Revision 01	
25 June 2020
 
68 patients have been randomized/enrolled to date
 
The protocol amendment 04 was approved on 16 June 2020. However, it was not distributed externally and was immediately followed by protocol amendment 4 revision 01, with the addition of an interim analysis. Protocol amendment 04 revision 01 was submitted to health authorities.
 
The following sections are affected: Section 9.15 Planned Interim Analysis

Amendment 04	
16 June 2020
 
68 patients have been randomized/enrolled to date
 
The management of study activities during the COVID-19 pandemic are detailed in Appendix O.
 
The following sections are affected: Section 3.1 General Study Design and Study Schematic Diagram Section 4.5 Rescreening Section 5.1.1.2 Dosing Visits and Dose Modification Appendix D. Quality Control and Quality Assurance Appendix E. Ethics

Amendment 03	
22 July 2019
 
No patients have been randomized/enrolled to date

Amendment 02	
16 April 2019
 
No patients have been randomized/enrolled to date

Amendment 01	
08 February 2019
 
No patients have been randomized/enrolled to date

The Summary of Changes to the Protocol includes the corresponding reason/justification for each change and is provided in [Section 16](#).

INVESTIGATOR AGREEMENT

Original Protocol Dated 06 December 2018

Clinical Study Protocol with Amendment 05

**IND number: 141519; NDA number: Not Applicable; BLA number: 761089;
EudraCT number: Not Applicable**

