2.4. Sample Size and Power Considerations

The sample size of 80 subjects per treatment group was selected based on expert consensus agreement at a scientific advisory board meeting; this sample size is expected to provide sufficient precision to estimate the treatment effect of fremanezumab versus placebo. Moreover, assuming a standard deviation (SD) of 2.2 for change from baseline in the weekly average of the daily average PI-NRS score, 80 patients per treatment group will provide at least 90% probability to observe the half length of the 95% confidence interval (CI) of the treatment difference between fremanezumab 225 mg sc or fremanezumab 675 mg sc and placebo less than 0.74. In total, 240 patients will be enrolled in this study in a 1:1:1 randomization ratio.

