6.2.2. Primary Efficacy Analysis

The primary efficacy endpoint will be analyzed using a MMRM model with change from baseline in the average of the daily average PI-NRS score over the past 24 hours at weeks 1, 2, 3, 4, 5, 6, 7, 8, 9, 10, 11, and 12 as the dependent variable, sex, age group at FM onset, week, treatment, and treatment by week interaction as fixed factors, and baseline average of the daily average PI-NRS score as a covariate. The heterogeneous autoregressive correlation structure [ARH (1)] for repeated observations within patients will be used, and the denominator degrees of freedom will be estimated using Kenward-Roger’s approximation. An adjustment for missing data due to lack of efficacy or adverse events assumes the PI-NRS scores will be on average return to baseline values. Missing data (due to early treatment discontinuation or missing e-dairy recording in an entire analysis week) will be imputed 500 times to generate 500 complete data sets using the SAS procedure PROC MI following the 3 steps below.

Notes, if ARH(1) does not converge, then simpler covariance structures with less parameters will be used in the following order until the model converges: autoregressive (1) (AR[1]); heterogeneous compound symmetry (CSH); and compound symmetry (CS).

Step 1: The monotone missing pattern will be induced by the Markov Chain Monte Carlo method in the PROC MI procedure using seed number 4751523.

The average of the daily average PI-NRS score up to and including week 12 will be imputed by using following SAS code to impute the arbitrary missing data and to make the missing data pattern monotonic:

```
PROC MI DATA=name NIMPUTE= 500 SEED=4751523 OUT= MI_MONOTONE;  
  BY TRT01PN AGEATFMONST SEX;  
  MCMC IMPUTE= MONOTONE;  
  VAR BASE WEEK1 ... WEEK12;  
RUN;
```

Where TRT01PN denotes the planned treatment group; AGEATFMONST denotes the age group at FM onset; BASE denotes the baseline average of the daily average PI-NRS score; WEEK1, . . . , WEEK12 denote the weekly average of the daily average PI-NRS score in weeks. In bold are the SAS key words.

Statistical Analysis Plan

Step 2: Once the arbitrary missing data are imputed, the following SAS code will be used to impute the monotone missing data.

The remaining missing data at subsequent weeks will be imputed using the regression method for the monotone pattern with seed number 4751523 and adjustment for covariates including baseline value and all values at preceding weeks.

```

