PROC MI DATA= MI_MONOTONE NIMPUTE= 1 SEED= 4751523
OUT= MI_COMPLETE;
  CLASS TRT01PN AGEATFMONSET SEX;
  MONOTONE REG;
  VAR TRT01PN AGEATFMONSET SEX BASE WEEK1 ... WEEK12;
RUN;
```

MI_COMPLETE will be transposed to a new data set (WEEKPI0) with each week as a row.

Step 3: Use by-week mean change from baseline to adjust those who discontinued treatment due to lack of efficacy (LOE) or adverse event (AE) before week 12.

The initially missing and now imputed data for patients who discontinued from the study drug due to LOE or AE will be center adjusted at the mean baseline value. That is, the final imputed score will be equal to the imputed score under missing at random minus the observed mean change from baseline score at the post baseline time point.

```
DATA WEEKPI;
  SET WEEKPI0;
  CHANGEi = AVALi - BASE;
  IF DTREAS IN ('LACK OF EFFICACY', 'ADVERSE EVENT') AND IMP= 1
  THEN DO;
    CHANGEi = CHANGEi - MWEEK_CHG;
  END;
RUN;
```

Where AVALi denotes the value of the post baseline weekly average of the daily average PI-NRS after missing data imputation; CHANGEi denotes the change from baseline after missing data imputation; MWEEK_CHG denotes the change from baseline calculated without missing data imputation; DTREAS denotes the reason for treatment discontinuation.

Step 4: Each of the 500 imputed data sets described above steps will be analyzed using the MMRM. SAS code is:

```
ODS OUTPUT LSMEANS= LS DIFFS = DIFF (WHERE = (week = _week));
PROC MIXED DATA= WEEKPI (WHERE= (WEEK>= 1));
  BY _IMPUTATION_;
  CLASS SUBJID TRT01PN WEEK AGEATFMONSET SEX;
  MODEL CHANGEi= BASE TRT01PN AGEATFMONSET SEX WEEK
    TRT01PN*WEEK/DDFM=KR;
  REPEATED WEEK/SUBJECT= SUBJID TYPE= ARH(1);
  LSMEANS TRT01PN*WEEK / DIFF CL;
RUN;
ODS OUTPUT CLOSE;
```

Statistical Analysis Plan

Where `_IMPUTATION_` denotes the numbering of imputations; `SUBJID` denotes the subject ID; `WEEK` denotes the analysis week (12 levels: weeks 1 to 12).

Step 5: The results from the 500 analyses from Step 4 will be combined using Rubin’s formulae (`PROC MIANALYZE`). The least square (LS) mean estimates for the mean change from baseline to each time point, as well as the difference of the estimates between the fremanezumab and placebo group, with the corresponding SE, p-value and associated 95% CI will be provided.

(a) For LS means

```
PROC SORT DATA= LS;  
  BY WEEK TRT01PN _IMPUTATION_ ;  
RUN;  
  
ODS OUTPUT PARAMETERESTIMATES= LSM_O;  
PROC MIANALYZE DATA= LS;  
  BY WEEK TRT01PN;  

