  MODELEFFECTS ESTIMATE;  
  STDERR STDERR;  
RUN;  
ODS OUTPUT CLOSE;
```

Where `ESTIMATE` and `STDERR` are LS mean and standard error from Step 4.

(b) For treatment difference, treatment difference CI and p-values

```
PROC SORT DATA= DIFF;  
  BY WEEK TRT01PN _TRT01PN _IMPUTATION_ ;  
RUN;  
  
ODS OUTPUT PARAMETERESTIMATES= DIFF_O;  
PROC MIANALYZE DATA= DIFF;  
  BY WEEK TRT01PN _TRT01PN;  
  MODELEFFECTS ESTIMATE;  
  STDERR STDERR;  
RUN;  
ODS OUTPUT CLOSE;
```

The observed data (ie, without imputation for missing data) will be summarized using descriptive statistics by analysis weeks (baseline, weeks 1 to 16).

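### The Kenward-Roger degrees of freedom stated for the primary analysis do not reach the pooled confidence intervals and p-values, because the pooling code passes no complete-data df (a small effect, under about 1.3%)

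*SAP*

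**What the plan says.** SAP 6.2.2 (Primary Efficacy Analysis) says of the primary MMRM that "the denominator degrees of freedom will be estimated using Kenward-Roger" (and the approximation of that name). Protocol 9.6.4.1 says the same. The Step 4 code delivers this in the model statement: "TRT01PN*WEEK/DDFM=KR".

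Step 5 combines the 500 sets of results by Rubin's formulae. It has two calls: one for the LS means, by week and treatment, and one for the treatment differences, "PROC MIANALYZE DATA= DIFF", by week and pair of treatments. Each names ESTIMATE as the effect and STDERR as its standard error. Neither contains EDF= or any df variable. The pooled LS means, differences, confidence intervals and p-values are the only model-based primary results that the SAP reports.

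SAP 18 (Changes to Analyses Specified in the Study Protocol) lists no change, and no section says that the Kenward-Roger df are set aside at pooling.

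**The concern.** Without EDF=, PROC MIANALYZE takes the complete-data df as infinite. With 500 imputations the pooled df are then so large that the critical value is 1.960. The df computed in Step 4 affect no reported interval or p-value, so the df sentence in SAP 6.2.2 describes something the printed code does not carry through.

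The omission also leaves two df conventions in one report. The FIQR and PROMIS analyses (SAP 6.3.1 and 6.3.5 to 6.3.7) are not imputed, so they take Kenward-Roger df straight from PROC MIXED. Every analysis that reuses 6.2.2 gets near-normal intervals: the primary endpoint, the rescue-medication sensitivity analysis (6.2.3), daily worst pain (6.3.4) and the per-protocol repeats. The primary objective is estimation, so the interval is the main product, and it gets the less conservative convention without explanation.

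**Working it through.** **Inputs from the documents.** m = 500 imputations. SAP 2.4: "assuming a standard deviation (SD) of 2.2 for change from baseline"; "80 patients per treatment group will provide at least 90% probability"; half-length for each dose against placebo, ending "fremanezumab 675 mg sc and placebo less than 0.74"; and "240 patients will be enrolled in this study in a 1:1:1 randomization ratio". The protocol's amendment history gives "153 patients have been randomized/enrolled to date" at Amendment 05, and the trial later stopped early, so the final number may lie well below 240.

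**Inputs assumed.** The complete-data df (ν₀) and the fraction of missing information (λ) are not in the documents. An approximate Satterthwaite calculation for a 12-week ARH(1) covariance, with between-week correlation from 0.5 to 0.95, gives week-12 df of about 166 to 195 for roughly 150 patients and 264 to 309 for roughly 240. A simple count of patients less model terms gives lower values, for example 150 − 8 = 142 and 240 − 8 = 232. The range 140 to 300 covers nearly all of these. λ is taken from 0.02 to 0.30.

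**The plan's own figure.** Half-length = t(0.975, 158) × S × √(2/80), with 158·S²/2.2² distributed as chi-square on 158 df. The probability of a half-length below 0.74 is 0.918, so the stated 90% reproduces. The planned standard error is 2.2 × √(2/80) = 0.348.

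**Pooled df as coded.** ν = (m − 1)/λ² = 499/λ². This is 12,475 at λ = 0.20 and 5,544 at λ = 0.30. The critical value is 1.960 throughout.

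**Pooled df with EDF=** (Barnard-Rubin). ν_obs = [(ν₀ + 1)/(ν₀ + 3)] × ν₀ × (1 − λ), and the adjusted df = 1/(1/ν + 1/ν_obs). For ν₀ = 142 and λ = 0.20: ν_obs = (143/145) × 142 × 0.8 = 112.0, and adjusted df = 1/(1/12,475 + 1/112.0) = 111.0.

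| ν₀ | λ | Adjusted df | t with EDF= | Interval as coded is narrower by | p = 0.050 would print as |
|---|---|---|---|---|---|
| 140 | 0.30 | 95.0 | 1.985 | 1.25% | 0.047 |
| 142 | 0.20 | 111.0 | 1.982 | 1.08% | 0.048 |
| 200 | 0.20 | 156.4 | 1.975 | 0.76% | 0.048 |
| 232 | 0.20 | 181.3 | 1.973 | 0.66% | 0.049 |
| 300 | 0.02 | 292.0 | 1.968 | 0.41% | 0.049 |

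At ν₀ = 100, a pessimistic value, the shortfall is 1.3% to 1.8%.

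**In scale points.** At standard error 0.348, the half-length moves from 0.682 to between 0.685 (ν₀ = 300, λ = 0.02) and 0.691 (ν₀ = 140, λ = 0.30), a change of at most 0.009. With 153/3 = 51 per arm, the standard error is 2.2 × √(2/51) = 0.436 and the largest change is 0.436 × (1.9853 − 1.9604) = 0.011.

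**Actual coverage.** Step 3 subtracts the observed mean change from the imputed values of patients who stop for lack of efficacy or an adverse event. Rubin's variance does not account for that shift. A simplified simulation used 80 per arm, one earlier week correlated 0.8 with week 12, 10% to 15% dropout for other reasons, and 3,000 runs per scenario. All dropout rates are assumed.

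| Lack-of-efficacy/AE dropout | Mean Rubin SE ÷ empirical SE | Coverage as coded | Coverage with EDF= |
|---|---|---|---|
| 0% | 1.02 | 95.1% | 95.3% |
| 5% | 1.07 | 96.6% | 96.8% |
| 10% | 1.09 | 96.6% | 96.8% |
| 15% | 1.16 | 97.6% | 97.8% |

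A second simplified simulation, also without EDF=, gave 94.7% to 94.8% with no such dropout and 95.0% to 97.0% at 3% to 10%.

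**The case against.** The strongest reply is that the code does what each sentence says. Kenward-Roger is assigned to the MMRM, and Step 4 uses it. Rubin's formulae are assigned to the combination, and Step 5 uses them. No sentence says that small-sample df govern the pooled interval, and the standard error carried forward still comes from the Kenward-Roger fit, so any adjustment of the standard error survives. As a matter of literal wording this stands. It does not settle the point. The pooled results are the only model-based primary results reported, Rubin's rules do not require infinite complete-data df, and a reader of 6.2.2 would expect the stated df to apply to what is reported.

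A reader might also infer that every primary interval is too short in the coverage sense, that p-values are always too small, or that the type I error is correspondingly inflated. The documents do not support that. The df effect taken alone runs in one direction, but turning it into an error rate requires Rubin's variance to be exact, and Step 3 breaks that assumption. In the simulations, coverage as coded was close to 95% with no lack-of-efficacy or adverse-event dropout and at or above 95% with it. There, adding EDF= moves coverage slightly further above nominal. The size of this offset depends on dropout rates that the documents do not give, so it is no justification for omitting the df either.

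Materiality is also low. The trial is an estimation-focused proof of concept with no multiplicity adjustment, already stopped for futility, and the stated precision target still reproduces. That argues for a low priority.

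**Conclusion.** The point holds as a gap between the stated df and the reported results. The Kenward-Roger df from Step 4 play no part in any pooled primary interval or p-value; the standard error from that fit does. For complete-data df of 140 to 300 and λ up to 0.30, both assumed, the intervals are about 0.4% to 1.2% narrower than with the stated df. That is under 0.01 PI-NRS points at the planned standard error and about 0.011 at worst with 51 per arm. A p-value of 0.050 would print as about 0.047 to 0.049.

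Under-coverage is not demonstrated. The omission and its size relative to the stated df are well supported; the net effect on coverage is uncertain. No conclusion of the trial is likely to turn on it. It is a minor correction, worth making because the SAP prints exact code that programmers will reproduce.

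**What to change.** Keep the DF column from the Step 4 LSMEANS and DIFFS outputs and supply it to both Step 5 calls as EDF=. EDF= takes one value for a whole call, while the calls run by week and treatment or contrast. So either loop over those groups, using for instance the mean DF over the 500 imputations in each, or use one conservative value such as the minimum DF.

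Add one sentence to SAP 6.2.2 saying that the Barnard-Rubin small-sample df, with the Kenward-Roger df as complete-data df, govern the pooled intervals and p-values. If normal-based pooling is intended, say that instead.

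Apply the same choice to the analyses that reuse 6.2.2: the rescue-medication sensitivity analysis, daily worst pain and the per-protocol repeats. The responder analyses in 6.3.3 use a GEE model without Kenward-Roger df, so this change does not concern them.

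The cost is a few lines of code and intervals wider by about 1% or less in most cases (at most about 1.3% over the assumed range). SAP 2.5.2 has the SAP approved before database lock and unblinding; made before then, the change cannot be influenced by the results.

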6.2.3. Sensitivity Analysis

Sensitivity analyses will be performed to address the assumptions in the primary model. The primary analysis will be repeated; however, the daily average PI-NRS scores measured on the days where the patient took rescue medication will be replaced as follows:

- If a patient took rescue medication once on a day, the PI-NRS score immediately before using rescue medication will be used as the daily average PI-NRS score for that day.

Statistical Analysis Plan

- If a patient took rescue medication more than once on a day, the mean value of PI-NRS scores immediately before using rescue medication uses for the day will be used as the daily average PI-NRS score for that day.

Note, if the PI-NRS score immediately before using rescue medication is not recorded, the daily average PI-NRS scores will not be replaced.

After the replacement, the baseline and post baseline weekly average of the daily average PI-NRS pain scores over the past 24 hours will be derived using formula [1], respectively. The data will be analyzed in the manner analogous to the primary endpoint as described in Section 6.2.2.

6.2.4. Sub-Group Analyses

Sub-group analyses will be performed on the primary and selected secondary efficacy endpoints for sex and age group at FM onset (<40 vs \geq 40 years) based on observed values only using descriptive statistics. The selected secondary endpoints are:

- Change from baseline to week 12 in the individual components of the Fibromyalgia Impact Questionnaire Revised (FIQR): symptom subscore, impact subscore, and functional subscore score
- Patient's Global Impression of Change (PGIC) by visit
- Change from baseline in the weekly average of the daily worst pain PI-NRS score by analysis week

Sub-group analysis will be based on mITT and/or PP analysis sets.

In addition, the primary endpoint will also be summarized by the following subgroups using descriptive statistics:

- PI-NRS BL \geq 5/<5,
- PI-NRS BL \geq 6/<6;
- PI-NRS BL \geq 7/<7;
- Enrollment prior to/post Study TV48125-PN-20028 protocol amendment 05;
- Enrollment prior to/post start of Covid-19 pandemic using the date of 26 Mar 2020 (site contact date) to represent the start of the pandemic;
- NSAIDs/no NSAIDs use at any time during the study (with NSAIDs to be defined by clinical review)

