5.7. Prior and Concomitant Medication or Therapy

5.7.1. Permitted Concomitant Medication or Therapy

Selective serotonin reuptake inhibitors or OTC medications are permitted if started at least 90 days prior to screening, have been on a stable dose for at least 90 days, and are expected to remain on a stable dose throughout the study, except for ≥ 60 mg/day of fluoxetine.

Over-the-counter medications used to treat depression or anxiety are permitted provided the dose has been stable for at least 90 days prior to screening and is not changed during the study.

For rescue treatment of FM-related pain, only acetaminophen up to 1000 mg per dose and not to exceed 3000 mg/day (for any indication) may be used, if needed, after recording the PI-NRS score in the e-diary. Use of nasal, inhaled, and topical steroids is permitted.

Nonsteroidal anti-inflammatory drugs are permitted provided the use has been stable (ie, per patient's usual dosing regimen) for at least 1 month prior to screening and will remain unchanged throughout the study.

Antihistamines are permitted for sleep. In addition, tricyclic antidepressants at low doses (amitriptyline [≤ 25 mg] or trazodone [≤ 150 mg]) or cyclobenzaprine (up to 10 mg), zolpidem (up to 10 mg), and melatonin may be used for sleep per the patient's usual dosing regimen, with no dose change 1 month prior to screening and throughout the study.

Concomitant medications permitted during the study include the following: 1) SSRIs (stable use), 2) the use of acetaminophen as a rescue medication up to 1000 mg per dose and not to exceed 3000 mg/day as a rescue medication for pain, 3) medications required for the treatment of any adverse events, 4) aspirin (maximum daily dose 325 mg) for cardiovascular prophylaxis, 5) nonsteroidal anti-inflammatory drugs (stable use), and 6) selected sleep medications.

If using marijuana (cannabis), cannabidiol, or other cannabinoids, regardless of route of administration, subjects should be instructed to keep their use at approximately the same dose/amount, route of administration, and frequency throughout the study.

No other FM medications (prescription, OTC, behind-the-counter, IMPs other than those permitted in this study, or vaccine) will be allowed during the study. For details of allowed medications, see [Appendix N](#).

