2. STUDY DESIGN

2.1. General Design

This is a 21-week, multicenter, randomized, double-blind, placebo-controlled, parallel-group study to evaluate the efficacy and safety of fremanezumab in adult patients with FM. Fremanezumab 225 mg, fremanezumab 675 mg, or placebo will be administered sc for 4 monthly doses. The study will consist of a 17- to 35-day screening period (Visit 1, phone contact, a Baseline Assessment Period Start [BAPS] Visit [Visit 2]), and a 16-week double-blind treatment period (Visits 3, 4, 5, 6, and 7). Patients enrolled in the study will be male or female patients with FM with an average of the daily average PI-NRS score of ≥ 4 and ≤ 9 during the 14-day baseline assessment period. Patients will be required to wash out of all prohibited concomitant medication(s) prior to the BAPS Visit (Visit 2).

[figure not shown]
Therefore, the total duration of patient participation in the study is planned to be 21 weeks, consisting of the screening period of up to 5 weeks (ranging from 17 to 35 days) and the double-blind treatment period of 16 weeks. The end-of-study (EOS) is defined as completion of the last visit of the last patient.

Note, there was the 14-week follow-up period prior to Study TV48125-PN-20028 protocol amendment 04.

The study schematic diagram is presented in [Figure 1](#).

Study procedures and assessments with their timing are summarized in Table 1 of the study protocol.

Figure 1: Overall Study Schematic Diagram

^a The screening period is up to 5 weeks and can range from 17 to 35 days. The duration of the washout period will be 7 to 19 days; suggested washout periods for commonly used analgesics are listed in the study protocol. Note: For Visits 4 and 5 (when at-home dosing is available), home visits are permitted for patients who are not able to go to the investigational center or if the investigational center staff are not able to see patients at the investigational center.

BAPS = Baseline Assessment Period Start; COVID-19 = Coronavirus Disease 2019; e-diary = electronic diary; EOS = end-of-study; EOT = end-of-treatment; PK = pharmacokinetic; sc = subcutaneous; V = visit.

The follow-up period (14 weeks) in the protocol was removed in Study TV48125-PN-20028 protocol amendment 04. The data collected in the follow-up period will be listed.

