6.2. Primary Efficacy Endpoint and Analysis

6.2.1. Definition

The primary efficacy endpoint is the change from baseline to week 12 in the weekly average of the daily average PI-NRS score over the past 24 hours.

Baseline is defined as the last 14 days before the first dose of IMP (Visit 3). The analysis weeks for post-baseline will be derived using rule described in [Table 2](#).

The baseline and post baseline weekly average of the daily average PI-NRS pain scores over the past 24 hours will be derived using formula [1], respectively.

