8.9. Concomitant Medications or Therapies

Concomitant therapies and medications, including medications that are taken on an as needed basis and occasional therapies, will be monitored during the study. Details of prohibited medications may be found in the study protocol. All concomitant medications will be coded using the WHO Drug Dictionary.

The incidence of concomitant therapies and medications will be summarized using descriptive statistics by therapeutic class category and preferred term. Patients are counted only once in each therapeutic class, and only once in each preferred term category. Concomitant therapies and medications will include all medications taken after the 1st dose of study drug administration up to the end of study as defined in the study protocol.

Similarly the prohibited medications will be summarized separately.

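### The NSAID subgroup in SAP 6.2.4 is not fixed before the first dose, so membership can depend on treatment and outcome (minor; define it by pre-dose use)

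*SAP*

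**What the plan says.** SAP 6.2.4 lists six added groupings, for which "the primary endpoint will also be summarized by the following subgroups using descriptive statistics". Five are fixed by enrollment or by the first dose: three baseline PI-NRS cut-offs, enrollment before or after Amendment 05, and enrollment before or after 26 March 2020. The sixth is "NSAIDs/no NSAIDs use at any time during the study (with NSAIDs to be defined by clinical review". The main subgroup factors in the same section, sex and age at FM onset, are also pre-treatment.

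SAP 6.2.1 sets the outcome: "The primary efficacy endpoint is the change from baseline to week 12 in the weekly average of the daily average PI-NRS score". SAP 2.1 gives a treatment period of 16 weeks. SAP 8.9 sets the medication window: "Concomitant therapies and medications will include all medications taken after the 1st dose of study drug administration up to the end of study".

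On permitted use, Protocol 5.7.1 states: "Nonsteroidal anti-inflammatory drugs are permitted provided the use has been stable", and requires that use to have been stable "for at least 1 month prior to screening and will remain unchanged throughout the study". The same section also permits "medications required for the treatment of any adverse events".

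**The concern.** A subgroup is interpretable when membership is settled before treatment can influence it. Here it is not. A patient who begins an NSAID in week 6 because pain is poorly controlled would leave the no-NSAID group for a reason tied to the outcome. If the drug works, that happens more often on placebo than on active treatment. A patient who begins one in week 14 is classified by something that happened after the endpoint was measured. The SAP does not say whether its phrase covers screening or weeks 13 to 16.

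At stake is the reading of one descriptive table. The no-NSAID group could lose some poor responders, unequally by arm, and the NSAID group could gain them. Differences between users and non-users could then be taken for effect modification or for an NSAID effect.

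**Working it through.** **Can membership change after randomization?** Full compliance with the stable-use rule would make on-study use nearly the same as baseline use. Three routes remain open:

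- Protocol 5.7.1 permits medication for adverse events, and this could be an NSAID.
- A patient may depart from the stable-use rule. Oral NSAIDs are not on the Appendix I prohibited list, so a new start does not clearly trigger the early-termination criterion for prohibited medication in Protocol 4.3.
- Under the rule in force before Amendment 04 (history, not an inconsistency), NSAIDs were allowed only for acute events, for up to 3 days. The amendment history records 68 patients enrolled by then. Their permitted use was event-driven.

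**The plan's own figure.** SAP 2.4 uses SD 2.2 and 80 per arm, and claims at least 90% probability of a 95% CI half-length below 0.74. The expected half-length is t(0.975, 158) × 2.2 × √(2/80) = 1.975 × 2.2 × 0.158 = 0.687. The probability is P(χ²₁₅₈ < 158 × (0.74/(1.975 × 0.158))²/2.2²) = 0.918. The claim reproduces, and SD 2.2 is carried forward.

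**Size of the selection.** Everything below except the SD is assumed: placebo mean change -1.2, true effect -0.70 in everyone (active mean -1.9), baseline-user share b = 0.30 unrelated to outcome, and no NSAID effect on pain. A fraction q of baseline non-users whose week-12 change is above zero start an NSAID, and no other non-users do.

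For an arm with mean μ and σ = 2.2:

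- p = Φ(μ/σ) is the share that worsens.
- E = μp + σφ(μ/σ) is that group's contribution to the mean.
- Never-user mean = (μ - qE)/(1 - qp).
- Ever-user mean = [μ - (1 - b)(μ - qE)]/[1 - (1 - b)(1 - qp)].

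Placebo gives p = 0.293 and E = 0.405. Active gives p = 0.194 and E = 0.236.

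With q = 0.40, on placebo:

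- Never-users: (-1.2 - 0.162)/(1 - 0.117) = -1.54.
- Ever-users: (-1.2 + 0.7 × 1.362)/0.382 = -0.65.

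| Scenario | Placebo never / ever | Active never / ever | Difference, never | Difference, ever |
|---|---|---|---|---|
| q = 0.40, effect -0.70 | -1.54 / -0.65 | -2.16 / -1.42 | -0.62 | -0.78 |
| q = 0.10, effect -0.70 | -1.28 / -1.03 | -1.96 / -1.77 | -0.68 | -0.73 |
| q = 0.40, no effect | -1.54 / -0.65 | same as placebo | 0 | 0 |

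Simulation of the first row gives -0.62 and -0.77. The shift from -0.70 is about 0.08 either way at q = 0.40. The share of non-users who start is qp: 12% on placebo and 8% on active at q = 0.40, and 3% and 2% at q = 0.10.

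**A second start model.** Here the odds of starting rise smoothly with worse change (log-odds 0.5 per point), 5 to 20% of placebo non-users start, 20 to 30% are baseline users, the placebo mean is -1.0 and the true effect is -0.74. The user minus non-user gap in the treatment difference is 0.08 to 0.15. With no true effect, or with starts unrelated to outcome, it is about zero. Across the outcome-related scenarios, placebo users look 0.33 to 1.14 points worse than placebo non-users.

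**Against the noise.** If 30% and 70% of the planned 80 fall in the two groups, there are 24 and 56 per arm:

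- 24 per arm: 2.013 × 2.2 × √(2/24) = 1.28.
- 56 per arm: 1.982 × 2.2 × √(2/56) = 0.82.

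Both are at least ten times the 0.08 shift.

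**Within an arm.** The placebo user versus non-user gap is 1.54 - 0.65 = 0.89 at q = 0.40 and 0.24 at q = 0.10, although no NSAID effect and no effect modification were built in.

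**The case against.** The strongest reply is that the protocol already limits the problem. NSAID use must be stable before screening and unchanged on study, acetaminophen is the only rescue allowed for FM pain, and patients agree not to start drug treatment for FM. With compliance, the two definitions nearly coincide. Noncompliance can also lead to early termination, and SAP 1.4 collects no further efficacy data after treatment discontinuation before week 12, so some starters would have no observed week-12 value. All of this stands and lowers the likely number of starters. It does not bring it to zero, given the three routes above.

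Second, the summary is descriptive, and Protocol 9.6.4.2 planned an analysis by analgesia use during baseline at the second interim. That analysis is broader than NSAIDs and belongs to the interim. It does show that a baseline definition was acceptable to the sponsor. Being descriptive limits the consequences, but selection moves means as well as p-values.

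Third, a reader might infer that patients who depart from stable use are those with poor pain control. The documents do not show this. New use may be for adverse events unrelated to FM pain, so the link to outcome is an assumption. A reader might also infer that the subgroup treatment effects are materially misstated. That needs a true effect, and the SAP was written after the study was stopped for futility. Futility does not prove a zero effect, but -0.70 is a favorable assumption here.

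**Conclusion.** The point holds as a minor one. NSAID use is the only factor in SAP 6.2.4 that can be set after randomization, and even after the outcome. Under the assumptions shown, the distortion of the treatment difference is at most about 0.08 points in either group in the -0.70 scenarios, and zero without a true effect. It would not be visible against intervals of ±0.8 to ±1.3. Those half-lengths use the planned 80 per arm, and fewer patients would widen them. The more exposed reading is the comparison of users with non-users within an arm, which could differ by 0.24 to 0.89 points through selection alone in the two worked scenarios. All sizes rest on assumed NSAID rates, an assumed placebo mean and an assumed link between worsening and starting.

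The documents do not support reading this as a threat to the trial's conclusion. The primary analysis in SAP 6.2.2 does not use NSAID status.

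**What to change.** In SAP 6.2.4, define the subgroup by NSAID use before the first dose, for example any use from day -14 to day -1, taken from the medication records at Visits 1 to 3. The window matters: SAP 5.5 counts as prior any medication taken before the first dosing day, so a bare prior-medication flag would also catch NSAIDs washed out before the baseline period. Tabulate NSAID starts after the first dose separately by arm, with timing before or after week 12. Settle the NSAID list before unblinding, since the SAP leaves it to clinical review without giving a date.

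The cost is a line or two of SAP wording and one small table, with no new data. SAP 2.5.2 has the plan and its amendments approved before database lock, which is when this change belongs. The small downside is that on-study starters no longer appear as users in the subgroup table, and the separate tabulation covers that.
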